If positive, this study would provide strong rationale for larger-scale clinical trials to determine effects of Fisetin on the following outcomes: 1) delay or prevention of progression to severe complications of CoV, including cytokine storm, ARDS, myocarditis with troponin leak, and long-term lung fibrosis, or for other infections in elderly or chronically-ill individuals, 2) treatment of severe complications of CoV or other infections in elderly or chronically-ill individuals, 3) treatment of nursing home participants who are infected with CoV (positive PCR test) despite immunization, and 4) delay, prevention, or treatment of multiple cellular senescence-associated conditions in the elderly, including individuals with chronic diseases.

# 3.2 Number of Subjects

Enroll and screen 250 subjects to accrue and randomize 150 men and postmenopausal women aged  $\geq$ 65 years old to be administered Fisetin (N=75) or placebo (N=75).

# 3.3 Duration of Participation

The study is estimated to complete enrollment within 18 months from study initiation; however, enrollment will remain open until the study goal is met. The duration of this study for each subject will be a maximum of 6 months. Study treatment will take approximately 4 out of 10 days. Subjects will be followed for up to 6 months or death, whichever comes first, including any available laboratory and chest imaging results if done as part of nursing home care. This will be done through study staff and health care providers in the nursing home or, if transferred to hospital, another facility, or home, by study staff contacting patients, their LAR, and/or their health care providers daily if feasible from Days 0 to 14 and at Days 30, 90 and 180 ( $\pm 14$ ; unblinding) after Fisetin vs. placebo was commenced if feasible, or from nursing home or hospital records. Adverse event reporting will be collected daily if feasible from the time of consent through Day 14. Adverse events will be assessed again at Days 30, 90 and 180, if possible. Subjects will not be required to return to the nursing home if discharged home or to another care setting.

# 3.4 Primary Study Endpoints

In this pilot study, the primary endpoint will be decreased progression of proven CoV infection in nursing home patients assessed using a 7 point scale adapted from the WHO Ordinal Scale for CoV Improvement (Appendix 1; Section 2; Primary Objectives) with unblinding at the end of the study.

# 3.5 Secondary Study Endpoints

In this pilot study of elderly adults in nursing homes who have proven CoV infection and no, mild, or moderate symptoms (Table 4), secondary endpoints will be: 1) safety and tolerability; 2) decreased blood senescent cells (blood CD3+ T cell assay for p16INK4A and SASP factors; if feasible); 3) cognitive function (from MDS section C, Cognitive Patterns, items C0100 – C1310; 4) function status/activities of daily living (from MDS Section G, Functional Status, items G0110-G0900; 5) functional abilities/frailty (from MDS section GG, Functional Abilities and Goals, items GG0130-0170 improved physical and cognitive function; 6) decreased circulating inflammatory markers and mediators (if feasible); 7) prevention or delay of deterioration in oxygenation status (SpO2/FiO2) if feasible; 8) reduced progression to intubation/ transition to end-of-life palliative care because of worsening condition, transfer to special nursing home unit admission because of worsening condition, hospital, ICU admission/ progression to ARDS/ myocarditis with troponin leak, death, delayed recovery, and delayed antibody response, and 9) decreased lung fibrosis during or at the end of the 6 month time subjects are in the study.

# 3.6 Primary Safety Endpoints

The primary safety endpoints are incidence of serious adverse events and hypersensitivity reactions. Safety assessments are undertaken with the measurement of safety laboratory tests and procedures, vital signs, and recording of adverse events.

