## 2 Study Objectives

#### 2.1 Primary Objectives

The primary objective is to test the efficacy of the senolytic drug (Fisetin) in preventing or delaying progression of CoV severity in nursing home patients with proven CoV according to a 7 point scale for nursing home CoV severity adapted from the WHO Ordinal Scale for Clinical Improvement of CoV\*:

- Not hospitalized nor on additional oxygen (compared to baseline), at baseline level of function (as assessed by activities of daily living).
- Not hospitalized nor on additional oxygen, but below previous level of function.
- Hospitalized or moved to a more intensive unit within the nursing home because of additional dysfunction (not simply because of positivity), but not requiring additional oxygen nor placed on an antiviral drug for worsening CoV symptoms.
- Hospitalized or moved to a more intensive unit within the nursing home and requiring additional oxygen (vs. baseline) and/ or placed on an antiviral drug for worseningCoV symptoms.

- Hospitalized or moved to a more intensive unit within the nursing home and requiring additional oxygen by ECMO or ventilator.
- Transferred to palliative care to provide end-of-life care.
- Death.

\*The WHO Ordinal Scale for Clinical Improvement of CoV (Appendix 1) is scored from 0 to 8 with 0 = no evidence of infection to 8 = death. Our adapted scale does not include scores 0 or 1, since no subjects in COVID-FIS will meet these criteria (e.g., all subjects have proven CoV infection, so none have "no infection").

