#### 9.1.3 Serious Adverse Event

Adverse events are classified as serious or non-serious. Serious problems/events can be well defined and include:

- Death includes all deaths, even those that appear to be completely unrelated to study drug (eg, a car accident in which a patient is a passenger).
- Life threatening adverse experience in the view of the investigator, the patient is at immediate risk of death at the time of the event. This does not include an AE that had it occurred in a more severe form, might have caused death
- Hospitalization Inpatient hospitalization is defined as admission to a hospital or an emergency room for longer than 24 hours. Prolongation of existing hospitalization is defined as a hospital stay that is longer than originally anticipated for the event or is prolonged due to the development of a new AE, as determined by the investigator or treating physician.
- Inpatient, new, or prolonged; disability/incapacity.
- Persistent or significant disability or incapacity.
- Birth defect/congenital anomaly.

and/or *pe*r protocol may be problems/events that in the opinion of the sponsor-investigator may have adversely affected the rights, safety, or welfare of the subjects or others, or substantially compromised the research data.

All adverse events that do not meet any of the criteria for serious will be regarded as **non-serious adverse events**.

Criteria for reporting SAEs must be followed for these events. See section regarding reporting of SAEs for more information on recording and reporting SAEs.

All study subjects will be provided with study team contact information 24/7. They will be educated on contacting the study team if any of these events occur. This will allow the study staff to be contacted if a serious adverse event occurs between study visits.

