# 9.1.9 Hospitalization, Prolonged Hospitalization, or Surgery

Any adverse event that results in hospitalization or prolonged hospitalization will be documented and reported as a serious adverse event unless specifically instructed otherwise in this protocol. Any condition responsible for surgery will be documented as an adverse event if the condition meets the criteria for an adverse event.

Neither the condition, hospitalization, prolonged hospitalization, or surgery will be reported as an adverse event in the following circumstances:

The following hospitalizations will not be considered SAE for this study:

- a visit to the emergency department or other hospital department <24 hours, that does not result in admission (unless considered an important medical or life-threatening event).
- elective surgery planned prior to signing consent.
- admissions as *per* protocol for a planned medical/surgical procedure.
- routine health assessment requiring admission for baseline/trending of health status (*e.g.*, routine mammogram).
- medical or surgical admission other than to remedy ill health and planned prior to entry into the study. Appropriate documentation will be obtained in these cases.

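### All-cause SAE incidence overlaps substantially with the efficacy outcome, and no by-arm comparison of SAEs other than COVID-19 progression is planned

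*Combined protocol and SAP*

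**What the plan says.** **Safety endpoint.** Section 3.6: "The primary safety endpoints are incidence of serious adverse events and hypersensitivity reactions". SAE incidence is thus one of two primary safety endpoints, and it is not limited by cause.

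**What counts as an SAE.** Section 9.1.3 says of death: "Death includes all deaths, even those that appear to be completely unrelated to study drug". On admissions it says: "Inpatient hospitalization is defined as admission to a hospital or an emergency room for longer than 24 hours". Section 9.1.9 adds: "Any adverse event that results in hospitalization or prolonged hospitalization will be documented and reported as a serious adverse event". Worsening of a pre-existing condition is itself an adverse event (9.1.2, 9.1.5), and every participant is infected at entry (4.1).

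**What is exempt.** The list in 9.1.9 that opens "The following hospitalizations will not be considered SAE for this study" covers short emergency visits and elective, per-protocol, routine or pre-planned admissions. Progression of COVID-19 is not on it.

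**Efficacy outcome.** Section 3.4 has progression "assessed using a 7 point scale adapted from the WHO Ordinal Scale for CoV Improvement". In section 2.1 the seventh level is death. Hospitalization is one route into levels 3 to 5, for example level 5: "Hospitalized or moved to a more intensive unit within the nursing home and requiring additional oxygen by ECMO or ventilator". Level 6 is "Transferred to palliative care to provide end-of-life care". Section 3.5 lists death and hospital and ICU admission again as secondary efficacy endpoints.

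**Safety analysis.** Section 8.2 plans adverse-event frequency tables by arm and Fisher or chi-squared tests on individual adverse events. It specifies no by-arm analysis of SAEs that leaves disease progression aside.

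**The concern.** A death or hospital stay from COVID-19 enters both the efficacy comparison and the SAE count. This weakens the SAE total as a safety measure in two ways.

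- If Fisetin works, disease SAEs fall in that arm and can cancel SAEs that the drug causes.
- If it does not work, a large disease background common to both arms makes a drug-caused excess hard to see.

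The plan's own expectations make a large disease share plausible: section 1.6 cites 25 to 50% COVID-19 mortality in nursing-home patients and anticipates no SAEs from the regimen. Safety and tolerability is a stated objective (2.2), and similar SAE totals in the two arms would be weak evidence for it.

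**Working it through.** **Inputs.** From section 8.1: 75 per arm, two-sided alpha 0.05, control participants spread equally over seven categories (1/7 each), log odds ratio 0.81. The documents do not give the share of levels 3-5 reached by hospital admission, the drug-caused SAE rate or the rate of other SAEs, so ranges are used for these.

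**Step 1: the plan's own figure.** Proportional-odds formula (Whitehead), 1:1 allocation: N = 12(z₀.₉₇₅ + z₀.₈₀)² / [(ln OR)²(1 − Σp̄³)], where p̄ is the mean of the two arms' category proportions. With OR 2.25, N = 147 for 80% power, and 150 participants give 80.9%. The stated 80% is reproduced.

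**Step 2: the Fisetin distribution.** Multiply the control cumulative odds of a better category by exp(0.81) = 2.248.

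- Death: control odds of not dying 6; 6 × 2.248 = 13.49; 1/(1 + 13.49) = 6.9%.
- Levels 3-5: cumulative through level 5, 2.5 × 2.248 = 5.620, giving 84.9%; through level 2, 0.4 × 2.248 = 0.899, giving 47.3%. The difference is 37.5% (control 3/7 = 42.9%).

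**Step 3: the drug-caused rate that equalizes the totals.** Let pC and pF be the proportions with a disease SAE. If the drug causes SAEs in a share x of the Fisetin participants without one, the totals are equal when x = (pC − pF)/(1 − pF).

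| Overlap | pC | pF | x | Extra Fisetin participants, 75(pC − pF) |
|---|---|---|---|---|
| Deaths only | 14.3% | 6.9% | 7.9% | 5.5 |
| Deaths + half of levels 3-5 | 35.7% | 25.7% | 13.5% | 7.5 |
| Deaths + all of levels 3-5 | 57.1% | 44.5% | 22.8% | 9.5 |

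As a cross-check, apply OR 2.25 to the mortality range in section 1.6. Deaths of 25% vs 12.9% would offset x = 13.9%, and 50% vs 30.8% would offset 27.8%.

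**Step 4: power when Fisetin has no efficacy.** With background b in both arms, the Fisetin rate is 1 − (1 − b)(1 − x). Two-proportion normal approximation, pooled variance under the null, 75 per arm:

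| Background b | Count it represents | x = 10% | x = 15% |
|---|---|---|---|
| 43% | all SAEs, if half of level 6 is also counted | 10% | 18% |
| 36% | all SAEs, deaths + half of levels 3-5 | 12% | 22% |
| 20% | other SAEs only (assumed) | 21% | 39% |
| 10% | other SAEs only (assumed) | 35% | 60% |
| 5% | other SAEs only (assumed) | 50% | 77% |

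Fisher's exact test gives somewhat less: 9% (16%) at 43%, and 41% (72%) at 5%.

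**The case against.** **No pooled SAE test is specified.** Section 8.2 tabulates adverse events and tests them individually. It sets no safety power and no criterion based on the SAE total. This stands: the power figures describe how informative the 3.6 endpoint would be if compared between arms, not a planned test. An unusual drug-caused event could show in the event-level tables. Those tests, however, split the events into small counts and do not analyse the endpoint that 3.6 names.

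**The overlap is partial.** In-house moves and palliative transfer do not by themselves meet the SAE criteria, and hypersensitivity is a separate primary safety endpoint. SAEs are collected to Day 180 and include events unrelated to COVID-19, whereas the 8.1 distribution is for Day 14. All of this stands. A reader might count all of levels 3 to 7 as SAEs, which gives 71% vs 53% and lets 40% be offset. The definitions in 9.1.3 do not support that, so it is only a ceiling.

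**Safeguards exist.** Investigators grade causality (9.3.1, 9.3.2), a DSMB sees unblinded data (9.8), and one stopping rule uses treatment-related deaths (9.6). These reduce the risk of missing a specific harm but do not supply the missing comparison. The grade for a possible relationship includes events that concurrent disease could also explain. No by-arm analysis of related SAEs is planned, and the stopping ground that 9.8 names for the DSMB is an excess of SAEs, the same mixed count.

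**All-cause SAEs measure net harm without attribution.** This also stands, and it is a reason not to replace the endpoint.

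**Conclusion.** The point holds as a gap in the planned safety analysis. All-cause SAE incidence overlaps substantially with efficacy, and nothing prespecified separates the two. Under the 8.1 assumptions, a drug-caused SAE rate of about 8%, 13.5% or 23% among the remaining Fisetin participants could leave the totals equal. These figures rest on equal control categories, the planned odds ratio, an assumed hospitalized share, and Day 14 levels standing in for SAEs collected over six months.

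A reader might go further and infer that the SAE endpoint mainly re-measures efficacy. The documents give no SAE rate, so that remains an inference: plausible from section 1.6, but not shown. The gain from separating the events is also uncertain. For an added 10% risk, power is about 50% if other SAEs run at 5%, but only 21% at 20%, and a high rate would not be surprising in residents whom section 1.6 describes as having limited life expectancy. The primary efficacy test and its stated power are unaffected.

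**What to change.** Keep all-cause SAE incidence as the 3.6 endpoint and leave every reporting rule unchanged.

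- On the existing adverse-event worksheet (9.3.1), add one item: the blinded investigator marks each SAE as COVID-19 progression or other, before unblinding.
- In 8.2, prespecify a by-arm row for participants with at least one SAE other than COVID-19 progression, with a 95% confidence interval for the difference, shown beside the all-SAE row.

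The cost is one worksheet item and one table row, with no new staff or procedure. The downside is that the classification needs judgement and could move drug-worsened COVID-19 out of the added row. The all-SAE row must therefore stay beside it, and neither row should be read alone.

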### 3.7 Identification of Source Data

Source data will be obtained from the nursing home record and documented in study-specific case report forms(paper and/or electronic data capture). No information in source documents about the identity of the subjects will be disclosed.

# 4 Subject Selection, Enrollment, and Withdrawal

#### 4.1 Inclusion Criteria

Subjects must meet *all* of the following inclusion criteria to be eligible for enrollment:

- 1. Men or post-menopausal women age  $\geq$ 65 years.
- 2. Current nursing home resident.
- 3. CoV severity of moderate or less OR SpO2  $\geq$  85% (on room air or  $\leq$  2 L of supplemental oxygen) at time of enrollment.
- 4. SARS-CoV-2 infection confirmed by mRNA-PCR test at Mayo Clinic or other CLIA certified laboratory, within 10 days before randomization.
- 5. Willing and able to provide written informed consent or have a legally authorized representative (LAR) who will provide informed consent.

#### 4.2 Exclusion Criteria

Subjects with *any* of the following exclusion criteria will not be eligible for enrollment:

### 4.2.1. General Exclusion Criteria

- 1. Presence of any condition that the Investigator or the subject's attending physician, physician's assistant, or nurse-practitioner believes would put the subject at risk or would preclude the patient from successfully completing the trial.
- 2. Pregnancy (note that only post-menopausal women will be enrolled).

# 4.2.2. Laboratory Exclusion Criteria

- 3. Total bilirubin >3X upper limit of normal or as *per* clinical judgment.
- 4. Serum aspartate transaminase (AST) or alanine aminotransferase (ALT) >4x the upper limits of normal or as *per* clinical judgment.
- 5. Hemoglobin <7 g/dL; white blood cell count  $\leq 2,000/\text{mm}^3$  ( $\leq 2.0 \times 10^9/\text{L}$ ) or  $\geq 20,000/\text{mm}^3$  ( $\geq 20 \times 10^9/\text{L}$ ); platelet count  $\leq 25,000/\mu\text{L}$  ( $\leq 25 \times 10^9/\text{L}$ ); absolute neutrophil count  $\leq 1 \times 10^9/\text{L}$ ; lymphocyte count  $< 0.3 \times 10^9/\text{L}$  at screening or as *per* clinical judgment.
- 6. Unstable (as *pe*r clinical judgment) major cardiovascular, renal, endocrine, immunological, or hepatic disorder.
- 7. eGFR <25 ml/ min/ 1.73 m^2 or as *per* clinical judgment.
- 8. Plasma and/or serum glucose >300 or as per clinical judgment.

# 4.2.3. Clinical History Exclusion Criteria

- 9. Human immunodeficiency virus infection.
- 10. Known active hepatitis B or C infection.
- 11. Invasive fungal infection.
- 12. Uncontrolled (as *per* clinical judgment) pleural/pericardial effusions or ascites.
- 13. History of diverticulitis or diverticulosis with GI bleeding, as *per* clinical judgment.
- 14. New/active invasive cancer except non-melanoma skin cancers as per clinical judgment.
- 15. Known condition associated with major immunodeficiency as *per* clinical judgment.

# 4.2.4. Medication Exclusion Criteria (see Investigator Brochure for additional information)

- 16. Known hypersensitivity or allergy to Fisetin.
- 17. Subjects taking any of the medications listed in the Investigator Brochure may participate if they are otherwise eligible AND the medication can be safely held

during the following times:

- Immediately before the 1st IP administration (Day 0) until at least 10 hours after the 2nd IP administration (Day 1).
- o Immediately before the 3rd IP administration (Day 8) until at least 10 hours after the 4th IP administration (Day 9).
- 18. Participation in other clinical trials involving treatment for COVID-19 (unless reviewed and approved by the Principal Investigator). Note that institutional standard of care treatment of COVID-19 including glucocorticoids, hydroxychloroquine, azithromycin, remdesivir, anti-spike antibodies, and/or convalescent plasma are not excluded from the study.

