**Fig. 2. Pre-existing senescence causes an exaggerated response to pathogens** *in vivo*. Elevenweek-old wild-type (blue) and progeroid  $Ercc1^{-/\Delta}$  (red) mice were injected with 500 ng/kg of LPS or vehicle (PBS) i.p. (N=4/ group). Twenty-four hours post-injection, mice were euthanized and tissues were collected. Total RNA was isolated from tissues and senescence and SASP marker expression was quantified in the (**A**) kidney and (**B**) liver by real-time qPCR using the ΔΔCt method. *Gapdh* was used as a control for gene expression analysis. (**C**) Circulating levels of IL-6 and MCP-1 were quantified in serum by ELISA. All values represent the mean ± SD. Statistical significance was determined by two-way ANOVA. \* p<0.05, \*\* p<0.01, \*\*\* p<0.001, \*\*\*\* p<0.0001, \*\*\*\* p<0.0001. (unpublished data, [name], [name], [name], [name]).

Amplifier/ Rheostat Hypothesis of Cellular Senescence: The SASP depends on the type of cell that became senescent, how senescence was induced, and its *milieu*. The SASP changes over time in response to internal (*e.g.*, transposons) and external cues (*e.g.*, PAMPs, DAMPs, glucocorticoids, SASP inhibitors such as rapamycin or metformin). PAMPs are particularly effective at exacerbating the SASP (Figs. 1&2), perhaps accounting for severe morbidity in previously highly-functioning elderly individuals with an increased (but quiescent) senescent cell burden that is activated by infections such as CoV or septicemia. Based on these considerations, we advanced an "Amplifier/ Rheostat Hypothesis" of cellular senescence: that the increased senescent cell burden in elderly and chronically ill patients contributes to their excessive, frailty/morbidity/mortality-inducing hyper-inflammatory (cytokine storm) response to infections that have much less cytokine-inducing effects in younger, previously healthy people (Fig. 3).

[figure not shown]

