Fig. 3. SASP Amplifier/Rheostat Hypothesis. Among the 10 leading causes of mortality in the elderly are influenza, pneumonia, genitourinary infections, and septicemia. The elderly and patients with cellular senescence-associated diseases (e.g., diabetes, dementias, smoking, asthma) are more susceptible to adverse outcomes in response to infections (e.g., ARDS, cytokine storm, myocardial damage with troponin leak, delirium, hypotension, thrombosis, delayed recovery) and develop a more exaggerated inflammatory state than young patients without pre-existing chronic diseases. These adverse outcomes of infections in the elderly or patients with senescence-associated chronic diseases have generally been attributed to immune system dysfunction or to chronic inflammation. Our "Amplifier/ Rheostat" Hypothesis is that PAMPs (e.g., LPS, viral antigens) cause a shift in the SASP of pre-existing senescent cells (SC) into a highly inflammatory, pro-apoptotic, pro-fibrotic SASP. This may not only exacerbate acute systemic inflammatory responses and cytokine

release by innate immune system cells (macrophages, dendritic cells, T lymphocyte subsets, neutrophils), but could also amplify spread of senescence to other cells. The resulting additional senescent cells may act to exacerbate and prolong inflammation, attenuate or delay recovery, lead to persistent frailty, cause long term tissue fibrosis if the afflicted individual survives long enough, and contribute to multi-organ failure ([name], [name], [name], October, 2018; unpublished).

Consistent with our Amplifier/Rheostat Hypothesis, we found CoV PAMPs exacerbate the SASP in quiescent human senescent cells, increasing secretion of factors underlying cytokine storm (IL-1 $\alpha$ , IL-6, IL-8), potentially contributing to frailty, hyper-inflammation, and ARDS (Fig. 4). This is consistent with the findings that rapalogs, glucocorticoids, and metformin, all of which inhibit the SASP, lessen CoV cytokine storm. However, unlike senolytics, these drugs have to be administered continuously, adding to off-target effects, especially in ill elderly patients. We also discovered SASP factors impair key viral defenses in human non-senescent cells (Fig. 5) and increase expression of the CoV viral entry proteins, ACE II and TMPRSS2 (Figs. 6&7).

[figure not shown]

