### 5.2.3. Standard of Care

Subjects will continue to receive institutional standard of care for the treatment of COVID-19 pneumonia and other conditions. The use glucocorticoids, Hydroxychloroquine, Azithromycin, Remdesivir, or Metformin is permitted. Subjects administered Rapamycin or other mTOR inhibitors, should they become standard of care, will be withdrawn unless the Rapamycin or other mTOR inhibitors are held for ≥5 days before the first dose of Fisetin on Day 0 until 1 hour after the final Fisetin dose on Day 9. Subjects started on other treatments for COVID-19 will continue to be followed if possible until the end of the study.

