#### 7.5 Research Labs

If possible, at each of the time points listed Appendix 2, 15 ml of blood will be collected to measure p16INK4A positive CD3+T lymphocytes - a biomarker of senescence and chronological aging. Blood will be tested for the CoV N and S1 antibodies by ELISA. The N antibody, if positive, indicates a past infection with CoV and is not affected by the RNA vaccines. The S antibody can become positive due to past CoV infection or CoV RNA vaccination. This will allow us to test both response to the vaccine in those subjects who are vaccinated as well as verifying previous infection/ adequate immune response to CoV infection. As is the case for MCL (Mayo Clinic Labs), samples will be handled in BSL-2 conditions.

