- Influence of demographic factors on outcomes: These endpoints of interest will tie in with earlier stated analyses, where we will overall assess how these demographic factors such as age, biological sex, and race and ethnicity may influence the outcomes. Since this study will be done at multiple different nursing homes that see different races and ethnicities of patients, these analyses can help to assess if there are any differential outcomes or interactions with factors on these outcomes.
- Senescent cell markers: The distribution of changes in the senescent cell markers will be summarized graphically stratified by treatment arms. Differences between the groups will be assessed using linear regression analysis at the time of interest, adjusting for baseline values. Mixed effects models, where feasible, will also be used to assess the treatment affect using all available measurements.

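### The SASP and inflammatory-marker models leave out entry glucocorticoid use, entry metformin use and age: a small loss of precision that prespecified covariates would recover

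*Combined protocol and SAP*

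**What the plan says.** **Drug effects.** Section 1.1 states that "rapalogs, glucocorticoids, and metformin, all of which inhibit the SASP, lessen CoV cytokine storm". Its list of external cues that change the SASP also includes "glucocorticoids, SASP inhibitors such as rapamycin or metformin".

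**Permitted use.** The note to criterion 18 in Section 4.2.4 says that "institutional standard of care treatment of COVID-19 including glucocorticoids, hydroxychloroquine, azithromycin, remdesivir, anti-spike antibodies, and/or convalescent plasma are not excluded from the study". Section 5.2.3 adds metformin: "The use glucocorticoids, Hydroxychloroquine, Azithromycin, Remdesivir, or Metformin is permitted". The same section treats the third named class differently: subjects on it "will be withdrawn unless the Rapamycin or other mTOR inhibitors are held for ≥5 days before the first dose of Fisetin".

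**Endpoints.** In Section 3.5, item 2 covers p16 in CD3+ T cells and SASP factors, and item 6 covers circulating inflammatory markers. Section 7.5 calls the p16 assay "a biomarker of senescence and chronological aging".

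**Analysis.** The Senescent cell markers bullet in Section 8.2.1 says: "Differences between the groups will be assessed using linear regression analysis at the time of interest, adjusting for baseline values". Mixed models are added where feasible. No medication or age term is named. The wording about other factors of interest appears only in the bullets on proportions and on time to event. Section 5.3 randomises without stratification. Remdesivir is the one co-treatment with a stated analysis, which is post hoc (Section 3.1).

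**Data.** Section 5.2.2 records all concurrent therapies, and Section 6.1 collects demographics and concomitant medication at screening.

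**The concern.** Section 1.3 describes target engagement as the critical outcome and says that blood pharmacokinetics will not be assayed. The blood markers are therefore the main evidence that Fisetin reached its target. By the protocol's own account, two permitted drugs act on some of those markers, and the models take no account of either.

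Two mechanisms need to be kept apart:

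- **Use at entry** adds variance to the markers. Covariates already on the record could remove it.
- **Glucocorticoids started after Day 0** may follow clinical worsening. If Fisetin works, such starts would be commoner on placebo. They would lower placebo SASP values at Day 14 and narrow the contrast.

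In either case, a weak marker result would be harder to interpret.

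**Working it through.** **1. The plan's own figure.** Section 8.1 gives 75 per group, two-sided alpha 0.05, seven equally likely control categories and a log odds ratio of 0.81 for 80% power. With V = N(1 − Σp̄³)/12, where p̄ is the mean of the two arms' category probabilities, N = 150 gives V = 12.20. Power is Φ(0.81 × √12.20 − 1.960) = 80.8%. The stated figure is reproduced, but it concerns the primary endpoint only. The documents give no SD, effect size or drug-use rate for the markers, so steps 2 to 4 rest on assumptions.

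**2. Reference effect for a marker.** With 75 per arm, the difference detectable with 80% power is (1.960 + 0.842) × √(2/75) = 0.457 SD. This assumes that all 150 give blood, although Section 7.5 collects it only where possible.

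**3. Entry use left out.** Assume a share p = 0.2 of users and a drug effect g of 0.5 to 1.0 SD.

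- Variance inflation is 1 + p(1 − p)g².
- Share of variance explained is p(1 − p)g² / [1 + p(1 − p)g²].
- Power is Φ(0.457 / (√inflation × √(2/75)) − 1.960).

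| g | Inflation | Variance explained | Power without covariate | Equivalent N, 150/(1 − R²) |
|---|---|---|---|---|
| 0.5 SD | 1.04 | 3.8% | 78.4% | 156 |
| 1.0 SD | 1.16 | 13.8% | 73.9% | 174 |

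Adjustment would return power to about 80%. The loss is smaller if a baseline marker value is available, because that value absorbs part of a stable drug effect.

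**4. Glucocorticoids started after Day 0.** The documents give no trigger for these drugs, so I take level 3 or worse on the seven-point scale as the group at risk.

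- Placebo: 5/7 = 71.4%, odds 2.5.
- Fisetin at OR 2.25: odds 2.5/2.25 = 1.11, so 52.6%.
- Gap: 0.188.
- Shrinkage = gap × uptake × drug effect, with the drug effect assumed to be 0.3 to 1.0 SD.

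| Uptake in that group | Shrinkage (SD) | Share of 0.457 SD |
|---|---|---|
| 25%, effect 0.3 SD | 0.014 | 3% |
| 50%, effect 1.0 SD | 0.094 | 21% |
| 100%, effect 0.3 to 1.0 SD | 0.056 to 0.188 | 12% to 41% |

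Deaths (level 7) would mostly give no Day 14 blood. Under the same inputs they are 14.3% of placebo and 6.9% of Fisetin. Among survivors, level 3 or worse is 66.7% v 49.1%, a gap of 0.176. The range at 25% to 50% uptake is still about 0.01 to 0.09 SD.

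**5. Is there a baseline marker value?** The population description in Section 1.1 and the assay list in Section 3.1 both mention blood before the first dose where feasible. Sections 6.1 and 6.2 list no research labs, Section 6.4 lists them at Day 14, and the research-lab row of Appendix 2 marks Day 14 only. As they stand, the only covariate in the marker model may not be collected.

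**The case against.** The case for leaving the plan alone has substance.

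- **Randomisation balances entry use on average.** This stands. A reader might infer that omitting these drugs biases the marker comparison. For entry use it does not; only precision is lost.
- **Keeping later standard care in an intent-to-treat comparison is legitimate.** This also stands. It is a treatment-policy comparison, not an error. It does need the arm-specific use of glucocorticoids beside it to be interpreted.
- **Baseline values absorb drug effects.** This is partly true, if those values exist. They cannot absorb a glucocorticoid started later.
- **The mTOR rule.** A reader might infer from the hold in Section 5.2.3 that the protocol protects its marker measurements from one SASP inhibitor and neglects two others. The text does not support that. The hold ends 1 hour after the last Day 9 dose, so it does not reach the Day 14 draw, and no such purpose is stated.
- **p16 counts.** A reader might extend the argument to all evidence of senolysis. Section 1.1 says that these drugs inhibit the SASP, not that they change p16+ T-cell counts, so the drug argument is not shown for that assay.
- **Age.** Section 8.2.1 plans a separate look at how demographic factors, including age, influence outcomes. That does not put age in the marker model, so the point survives as a lesser one.

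**Conclusion.** The concern holds as a minor point. The protocol names glucocorticoids and metformin as SASP inhibitors, permits both, and gives neither a place in the marker models. At 20% use and a drug effect of 0.5 to 1.0 SD, omitting entry use takes power for a 0.46 SD difference from 80% to about 78% or 74%, less if a baseline value is available.

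Later glucocorticoid starts could narrow the SASP contrast by about 0.01 to 0.09 SD at 25% to 50% uptake, provided they are commoner on placebo. A reader might take 0.06 to 0.19 SD as the likely shrinkage. That is a ceiling: it needs every participant at level 3 or worse to receive glucocorticoids, including those who die, and nothing in the documents says so.

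The drug argument is confined to SASP and inflammatory markers. These are secondary endpoints collected where feasible, and the primary ordinal analysis is unaffected.

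**What to change.** In the Senescent cell markers bullet of Section 8.2.1:

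1. For SASP factors and inflammatory markers, prespecify three fixed covariates in the linear and mixed models: glucocorticoid use at randomisation (yes/no), metformin use at randomisation (yes/no) and age. State that the bullet covers the inflammatory markers of Section 3.5, item 6.
2. For the p16 model, add age.
3. Keep the treatment-policy comparison. Do not adjust for use after randomisation, which treatment may affect. Tabulate glucocorticoid use at the Day 14 draw by arm, beside the marker result.
4. Reconcile Sections 1.1 and 3.1 with Section 6.2 and Appendix 2 on whether a pre-dose research sample is drawn.

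A sensitivity analysis that sets Day 14 values to missing after a later glucocorticoid start and then multiply imputes them should not be added. In the ceiling scenario it would discard up to 71.4% of placebo and 52.6% of Fisetin values, selected for worsening, and refill them mainly from participants who did not worsen, possibly without a baseline marker value to help.

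The cost is a few lines of text and up to three model degrees of freedom. The covariates come from records already planned. No change to permitted treatment is implied.
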